10.3.4 Vital Signs

Vital signs parameters include:

- weight (kg)
- systolic blood pressure (mmHg)
- diastolic blood pressure (mmHg)
- heart rate (beats/min)

Actual values and corresponding changes from baseline will be summarized by visit as descriptive statistics.

All vital signs data will be presented in a by-subject listing.

10.3.5 12-lead ECG

All ECGs will be sent to a local and central cardiology laboratory for reading and analysis. ECG measurement will include:

- RR, defined as the interval between 2 consecutive R waves (ms);
- Heart rate (HR, in beat per minute [bpm]), calculated as $60000 / RR$ (ms);
- P-R, defined as the interval between P and R waves (ms);
- QRS, defined as the distance between the Q and the S waves (ms);
- QT, defined as the interval between Q and T waves (ms);
- $QTcF$ (ms) = QT (ms) / RR (s)^{1/3}.

The triplicate values will be averaged in order to obtain one single value per subject and time point.

As per Protocol Amendment N° 2, central ECG reading will not be performed.

10.3.5.1 Central Tendency Analysis

Actual values for central assessment ECG parameters and their changes from baseline will be summarized using the descriptive statistics by time point. Ninety percent CIs of the mean will be presented as well. Standard deviation will be computed only if at least 3 records are available and 90% CIs only for cohorts in which at least 6 subjects are available.

Graphical representation of mean changes from baseline (with their 90% CIs upper bound when applicable) over time will be provided.

10.3.5.2 Categorical Analysis

The number and percentage of subjects presenting at least one value above the thresholds (irrespective of the cycle or time point) as defined in Table 3 will be computed per cohort and overall. All ECG collected (including unscheduled assessments) will be used for this analysis.

Table 3 - Thresholds for categorical analysis and corresponding flags for listings

Criteria	Flag
Actual values	
P-R > 220 ms	H
QRS > 120 ms	H
QTcF interval > 450 ms	B

QTcF interval > 480 ms	H
QTcF interval > 500 ms	P
Changes from baseline	
P-R relative change > 25%	I
QRS relative changes > 25%	I
QTcF interval increase from baseline > 30 ms	I
QTcF interval increase from baseline > 60 ms	I+

Flagging system will be used in listings to identify values above thresholds, also not necessarily related to clinically significant events, the flags can be interpreted as follows:

- B: Borderline value;
- H: High value;
- P: Prolonged value;
- I: Noticeable absolute increase from baseline;
- I+: Marked absolute increase from baseline.

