13. Subjects with a known history of uncontrolled or unstable angina or myocardial infarction within the last 6 months, unstable cardiac arrhythmias despite treatment (*subjects with a history of atrial fibrillation stabilized under treatment are allowed*), unexplained recurrent syncope, family history of sudden death from cardiac-related causes, congestive heart failure greater than New York Heart Association (NYHA) class II, uncontrolled diabetes, uncontrolled psychiatric disorders, severe ongoing infections or any other medical condition that might be aggravated by the treatment on evaluation.
14. Prolongation of QTcF interval to greater than 480 msec.
15. History of congenital long QT syndrome
16. History of another malignancy other than the primary tumor within the last 2 years, with the exception of completely resected basal or squamous cell skin cancer or any successfully treated in-situ carcinoma, or clinically insignificant prostate cancer without any treatment intent (either

treated or on active surveillance/watchful waiting). Other cancers within the last 2 years that are considered clinically insignificant by the treating physician should be discussed with the study Sponsor to assess eligibility.

17. Known infection requiring the systemic use of, for example, an antibiotic or antiviral agent.
18. Uncontrolled intercurrent illness or psychiatric illness/social situations that would limit compliance with study requirements.
19. If female, pregnant or breast feeding.
20. Unable to swallow and retain oral medications.
21. Known contraindication to enhanced magnetic resonance imaging (MRI) and/or computerised tomography (CT) scan.

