## Debio 1347-201 – Phase II basket trial in solid tumors harboring a fusion of FGFR1-3

- a) Pre-screening for tumor FGFR fusion/rearrangement will be made either locally at the study site in a certified laboratory or in a central laboratory using RNA or DNA-based NGS techniques prior to or during the 28-day screening period. Only subjects harboring FGFR fusions/rearrangements potentially leading to a functional FGFR aberrant protein may undergo the complete clinical screening required for study participation. The test will be made on adequate fresh tumor tissue slides (preferably) or, only if not possible, adequate unstained archival slides or tumor block.

**Of note:** A "liquid biopsy", e.g., ctDNA based test is acceptable for subject eligibility but then a pre-study treatment tissue sample is required for post-hoc confirmation of the fusion (see inclusion criterion No. 11 in Section 6.1).

**Of note:** Written informed consent for pre-screening will be obtained only from subjects who require a central assessment of FGFR status.

- b) BP and pulse rate will be taken after at least 5 minutes of supine rest.

- c) Triplicate 12-lead ECGs (PR, RR, QRS and QTcF intervals) will be recorded after at least 5 minutes of supine rest at the following time points: Screening, pre-dose Cycle 1 Day 1, pre-dose and 1, 3 and 7 hours post-dose Cycle 1 Day 28, pre-dose and 3 hours post-dose Cycle 2 Day 28, in all subsequent cycles at any time on Day 28 and at the time of disease progression and/or EOT.

**Of note:** All ECGs will be sent to a central cardiology laboratory for reading and analysis.

**Of note:** On Day 28 of Cycles 1 and 2, ECGs should be recorded maximum 20 min before each PK sample (see footnote g) below for PK sampling windows).

- d) **Hematology:** Complete blood count with differential (including ANC), hemoglobin, platelet count.

**Of note:** The screening sample can be combined with the pre-dose Day 1 sample if performed within 2 weeks prior to treatment start.

**Chemistry FASTING:** Total protein, albumin, indirect and total bilirubin, AST, ALT, ALP, electrolytes (sodium, potassium, calcium, magnesium), serum phosphate, serum creatinine, creatinine clearance, uric acid, bile salts. **On Cycle 1 Day 8:** Only serum phosphate. The assessment can be performed in a local laboratory.

**Of note:** The screening sample can be combined with the pre-dose Day 1 sample if performed within 2 weeks prior to treatment start.

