9 GENERAL STATISTICAL CONSIDERATIONS

9.1 General Conventions

The statistical analysis described below corresponds to analysis planned for the study. Any deviation from the planned analysis will be documented in clinical study report.

Continuous data will be presented in the form of descriptive statistics, as the number of observations, mean, standard deviation, minimum, 25th percentile (Q1), median, 75th percentile (Q3) and maximum.

Categorical data, including ordinal data, will be presented using contingency tables with absolute and relative frequencies. Missing will be considered as a category and included in the calculation of percentages, unless otherwise stated.

For time-to-event endpoints, Kaplan Meier (K-M) estimates will be provided and include number and percentage of events/censored, 25th (Q1), median and 75th (Q3) survival time and associated 95% confidence interval (CI, if applicable), survival rate and 95% CI at pre-specified time points. For the CIs, these will be Brookmeyer-Crowley for the survival time quartiles and Greenwood for the survival rate.

For PK parameters and concentrations, summary statistics in the tabulation will include number of non-missing value, number below the LOQ, mean, standard deviation, Q1, Q3, 90% CI of the arithmetic mean, coefficient of variation (CV%), median, minimum, maximum, geometric mean, 90% CI of the geometric mean, geometric standard deviation [calculated as: $\text{geo standard deviation} = \exp(\text{SDlog})$] and geometric CV% [calculated as: $\text{geo CV\%} = \text{SQRT}(\exp(\text{SDlog}^2) - 1) * 100\%$; where SDlog is the standard deviation of the log-transformed values].

The minimum and maximum will be reported to the same number of decimal places as the raw data recorded in the database. The mean, median, confidence intervals, Q1 and Q3 will be reported to one more decimal place than the raw data recorded in the database. The standard deviation will be reported to two more decimal places than the raw data recorded in the database. Percentages will be reported with one decimal place. The CV% is reported as a percentage with 1 decimal place.

Baseline measurement is the latest value collected prior to the administration of study drug.

All data analyses will be performed using SAS® statistical software version 9.4 or higher, R software version 3.3 or higher and NONMEM®.

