10.3.5.3 Morphological Analysis

A qualitative interpretation of the ECG will be performed by the cardiologist. This qualitative interpretation will provide a codification of the abnormalities detected on the recordings according to a code list grouping the abnormalities as:

- Q or Qs pattern;
- Axis and Voltage;
- Hypertrophy;
- ST depression and elevation;
- T/U wave abnormalities;
- AV conduction;
- Intraventricular conduction defects;
- Rhythm;
- Technical issue;
- Overall conclusion.

Number and percentage of subjects presenting at least one treatment emergent abnormality as defined by the code list will be computed per cohort and overall.

Treatment-emergent abnormality will be defined as any abnormality not already reported on the baseline ECG.

All treatment emergent abnormalities will be listed. Individual data listings will be displayed sorted by cohort, subject, and time-point, a flag will be added to identify values above thresholds as presented in Table 3.

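### The absolute-value rows of the ECG categorical table mix pre-existing values with post-dose ones, mainly for QTcF > 450 ms, QRS > 120 ms and P-R > 220 ms

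*SAP*

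**What the plan says.** SAP 10.3.5.2 sets the ECG thresholds in its Table 3. Five rows are absolute: P-R > 220 ms, QRS > 120 ms, and QTcF > 450, > 480 and > 500 ms. Four are relative to baseline: P-R and QRS change > 25%, and QTcF increase > 30 and > 60 ms. The statistic, per cohort and overall, is "The number and percentage of subjects presenting at least one value above the thresholds (irrespective of the cycle or time point". The data source is stated without limit: "All ECG collected (including unscheduled assessments) will be used for this analysis".

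Triplicate ECGs are scheduled "at the following time points: Screening, pre-dose Cycle 1 Day 1", then on treatment (Protocol Table 8-1, footnote c; repeated in SAP 13.7).

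The only numerical ECG limit at entry is exclusion criterion 14 (Protocol 6.2): "Prolongation of QTcF interval to greater than 480 msec". No criterion in Protocol 6.1 or 6.2 limits P-R or QRS.

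The SAP defines baseline in 9.1 ("Baseline measurement is the latest value collected prior to the administration of study drug") and a treatment period in 9.4. Section 10.3.5.2 applies neither to the absolute rows. For morphological findings, 10.3.5.3 says: "Treatment-emergent abnormality will be defined as any abnormality not already reported on the baseline ECG".

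**The concern.** An absolute-threshold count in a drug safety table is normally read as what was seen under treatment. As specified, each of these counts adds two groups: subjects who entered above the limit, and subjects who rose above it after dosing. The table does not show how many are in each.

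This matters more here than in a controlled trial. QTcF is the safety measure named in the secondary objectives. The study has one arm, so no comparator shows the background rate, and SAP 10.6 itself notes that placebo effects on QTcF could not be evaluated. The concentration-QTcF model that would address the question more directly is conditional and may not be run.

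Elsewhere the SAP does separate baseline from later findings. Adverse events must start or worsen after first dose (10.3.2), graded laboratory values get baseline-to-worst shift tables (10.3.3), and morphological abnormalities must be absent from the baseline ECG (10.3.5.3).

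**Working it through.** The plan states no expected rate, baseline prevalence or QTcF distribution, so it has no figure to reproduce. The check has one step from the text and three illustrations.

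**1. From the text alone.** Take an eligible subject with a pre-dose QTcF of 465 ms. Criterion 14 admits the subject, because 465 is not above 480. The pre-dose ECG is collected, so it enters the count. It exceeds the row "QTcF interval > 450 ms", and one value at any time point is enough. The subject is counted even if every later value is below 450 ms. The same holds for a pre-dose QRS of 130 ms, since no entry criterion limits QRS. This step needs no assumption.

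**2. Arithmetic.** Let b be the share above threshold before dosing and q the share of the remaining subjects who newly cross afterwards. The SAP rule reports b + (1 − b)q. A new-onset count, with subjects at or below threshold at baseline as denominator, reports q. Both inputs are assumed.

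| b | SAP rule, q = 0 | SAP rule, q = 5% | SAP rule, q = 10% |
|---|---|---|---|
| 5% | 5.0% | 9.8% | 14.5% |
| 10% | 10.0% | 14.5% | 19.0% |
| 20% | 20.0% | 24.0% | 28.0% |

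With the 63 evaluable subjects of SAP 9.3 (the final safety N is not given) and q = 0, the rule counts 63 × b = 3.2, 6.3 or 12.6 subjects. The new-onset count is zero.

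**3. Simulation with zero drug effect, QTcF > 450 ms.** Assumed: between-subject SD 18 ms, within-subject SD 8 ms, and nine ECG time points (screening, Cycle 1 Day 1 and seven on treatment). Subjects with screening QTcF above 480 ms are excluded, and Cycle 1 Day 1 is taken as baseline.

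| Assumed mean QTcF | Above at baseline | Above on any ECG (SAP rule) | Above on any post-dose ECG | Newly above, among those ≤ 450 ms at baseline |
|---|---|---|---|---|
| 410 ms | 2.1% | 6.5% | 5.8% | 4.2% |
| 420 ms | 6.3% | 16.5% | 15.2% | 10.2% |
| 430 ms | 15.1% | 32.8% | 30.8% | 19.8% |

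The share of counted subjects already above at baseline is 2.1/6.5 = 32%, 6.3/16.5 = 38% and 15.1/32.8 = 46%. With eight on-treatment ECGs instead of seven, it is 2.1/6.8 = 31%, 6.2/16.9 = 37% and 14.9/33.3 = 45%.

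Two things follow. Dropping the pre-dose ECGs alone changes little (6.5% to 5.8%, 16.5% to 15.2%, 32.8% to 30.8%), because a subject who starts above 450 ms usually has a later value above it too. Most of the reduction comes from the baseline condition. Even then, 4.2% to 19.8% appear as new crossings with no drug effect, from ordinary variability over repeated ECGs.

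**4. The higher QTcF rows.** With eight on-treatment ECGs, the SAP rule gives 0.09%, 0.42% and 1.6% above 480 ms. A new-onset rule gives 0.07%, 0.35% and 1.3% of all subjects. Above 500 ms both rules give at most 0.02%. Criterion 14 already does most of the work in these rows.

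**The case against.** The strongest reply is that the SAP claims less than a reader might infer.

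- **Label.** The rows are headed as actual values and are not called treatment-emergent. The text adds that flagged values need not be clinically significant. This stands. A reader might infer that the SAP presents these subjects as having crossed a threshold on drug, but the document does not say so. The defect is an undifferentiated count.
- **Baseline adjustment exists in the same table.** Rows such as "QTcF interval increase from baseline > 30 ms" are net of each subject's own baseline. Central tendency (10.3.5.1) reports change from baseline with 90% intervals, and the by-subject listings show when each flagged value occurred. This also stands. It would be too strong to say that 10.3.5.2 and 10.3.5.3 follow opposite rules, because the first contains both kinds of row. But a separate > 30 ms row does not show which subjects in the > 450 ms row were above it at entry.
- **Direction and consequence.** The rule can overstate a QT signal but not hide one. The table feeds no decision: the only QT decision rule is in 10.6.4, on model-predicted change from baseline. The primary endpoint is untouched. All of this stands and limits the weight of the point.
- **The repair does not isolate a drug effect.** Correct. Variability alone produces new crossings, so the repaired count should not be read as drug-caused either.

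**Conclusion.** The point holds as a matter of safety reporting. Subjects above 450 ms QTcF, 120 ms QRS or 220 ms P-R before dosing are counted regardless of what follows. These three absolute rows therefore mix entry status with post-dose findings and can overstate exceedances. That conclusion rests only on the text.

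The size does not. The documents give no QTcF mean, SD or baseline prevalence. The figure of roughly 30% to 45% already above 450 ms at baseline depends on the assumed mean of 410 to 430 ms, the two SDs and the number of ECGs. A reader might take it as a property of the plan, which the documents do not support. No size is offered for P-R or QRS, because nothing in the documents bears on it.

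The > 480 and > 500 ms rows are little affected, and the change-from-baseline rows are not affected. The change is worth making because it is cheap and the trial has no control arm. It does not threaten the main conclusions.

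**What to change.** In SAP 10.3.5.2, for the five absolute-value rows of Table 3:

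1. Use only ECGs recorded after the first dose, including unscheduled ones.
2. Count subjects newly above each threshold among those at or below it at baseline, using the SAP 9.1 definition, and make that group the stated denominator.
3. Show the number already above the threshold at baseline on a separate line. A baseline-to-worst shift table, as already planned for laboratory data, would serve equally well.
4. Add a sentence that, without a control arm, new crossings include ordinary variability over repeated ECGs.

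Leave the change-from-baseline rows as they are, and keep the raw flags in the listings. The entry criterion is not in question. The cost is a few lines of SAP text, one programming condition and a table-shell change; all the data are already collected.

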10.3.5.3 Morphological Analysis

A qualitative interpretation of the ECG will be performed by the cardiologist. This qualitative interpretation will provide a codification of the abnormalities detected on the recordings according to a code list grouping the abnormalities as:

- Q or Qs pattern;
- Axis and Voltage;
- Hypertrophy;
- ST depression and elevation;
- T/U wave abnormalities;
- AV conduction;
- Intraventricular conduction defects;
- Rhythm;
- Technical issue;
- Overall conclusion.

Number and percentage of subjects presenting at least one treatment emergent abnormality as defined by the code list will be computed per cohort and overall.

Treatment-emergent abnormality will be defined as any abnormality not already reported on the baseline ECG.

All treatment emergent abnormalities will be listed. Individual data listings will be displayed sorted by cohort, subject, and time-point, a flag will be added to identify values above thresholds as presented in Table 3.

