Of note: A "liquid biopsy", e.g., ctDNA based test is acceptable for subject eligibility but then a pre-study treatment tissue sample is required for post-hoc confirmation of the fusion (see inclusion criterion No. 11 in Section Error! Reference source not found.).

Of note: Written informed consent for pre-screening will be obtained only from subjects who require a central assessment of FGFR status.

b) BP and pulse rate will be taken after at least 5 minutes of supine rest.

c) Triplicate 12-lead ECGs (PR, RR, QRS and QTcF intervals) will be recorded after at least 5 minutes of supine rest at the following time points: Screening, pre-dose Cycle 1 Day 1, pre-dose and 1, 3 and 7 hours post-dose Cycle 1 Day 28, pre-dose and 3 hours post-dose Cycle 2 Day 28, in all subsequent cycles at any time on Day 28 and at the time of disease progression and/or EOT.

Of note: All ECGs will be sent to a central cardiology laboratory for reading and analysis.

Of note: On Day 28 of Cycles 1 and 2, ECGs should be recorded maximum 20 min before each PK sample (see footnote g) below for PK sampling windows).

d) **Hematology:** Complete blood count with differential (including ANC), hemoglobin, platelet count.

Of note: The screening sample can be combined with the pre-dose Day 1 sample if performed within 2 weeks prior to treatment start.

Chemistry FASTING: Total protein, albumin, indirect and total bilirubin, AST, ALT, ALP, electrolytes (sodium, potassium, calcium, magnesium), serum phosphate, serum creatinine, creatinine clearance, uric acid, bile salts. **On Cycle 1 Day 8:** Only serum phosphate. The assessment can be performed in a local laboratory.

Of note: The screening sample can be combined with the pre-dose Day 1 sample if performed within 2 weeks prior to treatment start.

Note regarding safety laboratory assessments: In the case of a significant laboratory abnormality or clinical or laboratory evidence of toxicity, the Investigator will collect additional samples for repeat or additional analyses at appropriate intervals. The subject will be closely followed until sufficient information has been obtained to determine the cause of the abnormality or the value has returned to an acceptable level. Appropriate remedial measures should be taken and the response recorded. Any clinically relevant change from baseline onwards must be recorded on the AE page of the eCRF.

e) Urinalysis: Red blood cells/hpf, white blood cells/hpf, casts/hpf and protein...

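### Read literally, SAP 10.3.5.3 lets a recording fault alone count as a treatment-emergent ECG abnormality, because technical codes are not excluded from the morphology count

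*SAP*

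**What the plan says.** SAP 10.3.5.3 describes the cardiologist's reading as follows: "This qualitative interpretation will provide a codification of the abnormalities detected on the recordings according to a code list grouping the abnormalities as", and then gives ten headings. The first eight, from the Q-wave pattern to rhythm, are cardiac findings. The ninth is "Technical issue" and the tenth is "Overall conclusion".

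The planned summary is: "Number and percentage of subjects presenting at least one treatment emergent abnormality as defined by the code list will be computed per cohort and overall". The rule that makes a code treatment-emergent is: "Treatment-emergent abnormality will be defined as any abnormality not already reported on the baseline ECG". The section also lists all treatment-emergent abnormalities by subject.

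Three other places bear on the count:

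- SAP 9.1 fixes the reference point: "Baseline measurement is the latest value collected prior to the administration of study drug".
- SAP 13.7, footnote c, schedules triplicate ECGs at screening, before the first dose, then "pre-dose and 1, 3 and 7 hours post-dose Cycle 1 Day 28, pre-dose and 3 hours post-dose Cycle 2 Day 28", once per later cycle, and at progression or end of treatment (EOT).
- SAP 10.3.5 averages triplicate values to one per time point. It gives no rule for combining morphology codes across the three tracings.

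The protocol synopsis says only that a morphological analysis will be done.

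**The concern.** A technical issue describes the recording, not the heart. The SAP introduces all ten headings as groups of abnormalities and then lets the code list define the count. A programmer following the text would therefore flag a subject who has an artefact or lead problem on one later tracing, a clean baseline and no new cardiac code.

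The result is a reported cardiac safety percentage that mixes recording quality with cardiac findings. The study is single-arm, so there is no control percentage to show how much of the figure is artefact. The opportunity is also uneven: baseline is one time point, while a subject who completes two cycles has several later ones.

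**Working it through.** **Text check.** Four steps follow from SAP 10.3.5.3 alone.

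1. The list groups abnormalities, and technical issue is one of the groups.
2. The numerator is any subject with at least one treatment-emergent abnormality defined by that list.
3. Treatment-emergent means absent from the baseline ECG, with no restriction to cardiac groups.
4. No other section of the SAP or protocol excludes technical codes or says how an uninterpretable tracing is handled.

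The numerator as written is thus the union of subjects with a new cardiac code and subjects with a new technical code. A union cannot be smaller than its cardiac part, so the rule can only raise the share.

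**Size.** The plan states no figure to reproduce. What follows is illustration only.

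Inputs from the documents (SAP 13.7, footnote c; SAP 9.1):

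- Post-baseline time points for a subject who completes two cycles: 4 on Cycle 1 Day 28 + 2 on Cycle 2 Day 28 + 1 at progression/EOT = 7, or 7 × 3 = 21 tracings.
- Baseline: 1 time point, or 3 tracings.

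Assumptions, which the documents do not give: a fault rate q of 1% to 5% per reading, and faults independent of each other and of cardiac findings.

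The gross chance of an emergent technical code is no fault at baseline and at least one later:

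P = (1 − q)^b × [1 − (1 − q)^m]

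with b = 1, m = 7 if coded per time point, and b = 3, m = 21 if coded per tracing. For q = 1%:

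- per time point: 0.99 × (1 − 0.99^7) = 0.99 × 0.0679 = 0.067
- per tracing: 0.99^3 × (1 − 0.99^21) = 0.9703 × 0.1903 = 0.185

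| Assumed fault rate | Per time point | Per tracing |
|---|---|---|
| 1% | 6.7% | 18.5% |
| 2% | 12.9% | 32.5% |
| 3% | 18.6% | 43.1% |
| 5% | 28.7% | 56.5% |

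**Gross to net.** A technical code changes the result only for a subject with no new cardiac code. If the true share with a new cardiac code is π, the reported share is π + (1 − π) × P. With an assumed π of 20% and q = 1%:

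- per time point: 0.20 + 0.80 × 0.067 = 25.4%, a rise of 5.4 percentage points
- per tracing: 0.20 + 0.80 × 0.185 = 34.8%, a rise of 14.8 percentage points

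**Fewer ECGs.** A subject who leaves between Cycle 1 Day 28 and Cycle 2 Day 28 has 4 + 1 = 5 post-baseline time points. One who leaves before Cycle 1 Day 28 has 1. Per time point at q = 1%, the gross chance falls from 6.7% to 0.99 × (1 − 0.99^5) = 4.9%, and to 0.99 × 0.01 = 1.0%.

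**The case against.** The strongest objection is that the individual codes are not in the documents; only the ten headings are. A heading for the overall conclusion would naturally also hold a normal verdict. If so, not every code is an abnormality, and the full list may already separate the two. This stands in part. It means one cannot state that technical codes will be counted, only that the SAP as written counts them and excludes nothing.

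Several stronger readings are tempting and are not supported:

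- *That the overall conclusion also inflates the count.* An abnormal verdict would normally follow a code in another group, and a repeated code adds no subject to an at-least-one count. This group is mainly redundant.
- *That a large fraction of subjects, up to about half, would be flagged falsely.* The high figures need per-tracing coding, a 5% fault rate and independent faults. The documents give none of these. Faults that cluster within a triplicate would lower the subject-level share.
- *That the seven-time-point subject is typical.* In the Phase I dose escalation (Protocol 3.3.2), median treatment was 7.3 weeks, short of the 8 weeks that make two cycles. That was a different population, but it warns against the presumption.
- *That the QTcF safety conclusion is at risk.* None of the ten groups is a QT group. QTcF is handled in SAP 10.3.5.1, 10.3.5.2 and 10.6, and none of these uses this count.
- *That longer-treated subjects are made to look worse.* The SAP makes no such comparison; it reports per cohort and overall. Any at-least-one summary rises with the number of ECGs.

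It also stands that the consequence is limited. The row is descriptive, with no test or decision rule attached, and the listing would let a reader find subjects flagged for a technical issue alone. Protocol Amendment 2 stopped central ECG reading, so it is uncertain how many ECGs receive cardiologist coding.

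**Conclusion.** The point holds as a wording defect with a small consequence. On the plain text, a subject whose only new code is a recording fault counts as having a treatment-emergent ECG abnormality. Relative to a count of cardiac groups, the bias can only be upward.

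Its size cannot be established from the documents. The illustration gives a gross chance of roughly 7% to 29% per time point, or 18% to 57% per tracing, for assumed fault rates of 1% to 5%. It rests on independent faults and 7 post-baseline time points. The net rise in the reported share is smaller, and subjects with fewer ECGs have a lower chance. ORR, alpha and power are not touched.

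**What to change.** In SAP 10.3.5.3, restrict the count of subjects with at least one treatment-emergent abnormality to the eight cardiac groups, from Q or Qs pattern through rhythm. List technical issues separately as a data-quality item. Report the overall conclusion on its own and do not count it as an abnormality. It would help to state in the same place how morphology codes are combined across a triplicate.

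The cost is one sentence in the SAP, or two with the triplicate rule, and a filter on codes already collected. No new data are needed.
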